7.7.4. Sensitivity Analyses

Three sensitivity analyses are planned to explore the impact of censoring due to treatment switch, censoring from analyses of safety endpoints due to occurrence of any cancer type, and potential misclassification of the primary endpoints based on use of the developed algorithms.

Specifically, the main analyses for the primary and secondary endpoints will be performed including person-time after treatment switch, and the main analysis for the primary endpoints only (endometrial hyperplasia and endometrial cancer) will be performed including patients who had been censored due to cancer occurrence. The IR estimate for each primary outcome (endometrial cancer and endometrial hyperplasia) will be corrected for the PPV of the outcome algorithm as identified through validation. This will be done by multiplying the number of observed cases by the PPV point estimate, and will be presented with a 95% CI.

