Automated data from the HIRD will be linked to the US National Death Index (NDI) to ascertain mortality endpoints, including all-cause mortality and mortality specific to study endpoints of interest. Medical records (for a random sample of 400 potential cases) will be used to refine and validate algorithms for identification of the primary endpoints (endometrial hyperplasia and endometrial cancer). For development of the endometrial endpoint algorithms, clinical evidence available in the medical record, which includes all results of endometrial biopsies and clinician evaluations, will be considered the gold standard definition of case status against which the claims-based algorithm's performance will be measured.

Study size: Hazard ratios (HRs) and their 95% confidence intervals (CIs) expected to be observed in this study were estimated. Endometrial hyperplasia and endometrial cancer are defined as the primary endpoints and were used for these calculations. The number of *Duavee* users in HIRD during the study period has been projected based on Pfizer commercial forecasts only; no patient data are currently available. Estimates of E+P HRT use were obtained based on pilot analyses of the HIRD from the last three years. For Year 1 of the US PASS, the 95% CI of the HR for the risk of endometrial hyperplasia is projected to lie between 0.44 and 2.26 (assuming the true HR=1.0) indicating that the study would be able to rule out an HR greater than 2.26. For Years 2 and 3, the CIs for endometrial hyperplasia risk in the study is projected to lie between (0.64 and 1.56), and (0.72 and 1.39), respectively. This indicates that the study would be able to rule out an HR greater than 1.56 at two years and greater than 1.39 at three years.

Data analysis: Analyses will focus on the comparison between women initiating either *Duavee* or E+P HRT. Baseline characteristics will be compared across the two cohorts of new users to assess potential confounding variables. For each safety endpoint (venous thromboembolism [VTE], stroke, coronary heart disease [CHD], breast cancer, ovarian cancer, endometrial hyperplasia, and endometrial cancer, etc.), univariate and adjusted HRs will be estimated that compare incidence of the first occurrence of each safety event between *Duavee* and E+P HRT users.

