using Receiver Operating Characteristic (ROC) curves to assign a threshold probability (10). A second set of 200 medical records will then be obtained by randomly selecting 200 women meeting the refined, score-based algorithm from the population of women using E+P HRT prior to the study period. This validation dataset will be used to assess the PPV of Algorithm 2 (1). The PPV will be calculated as the number of algorithm-identified events confirmed as true cases via medical record review divided by the total number of algorithm-identified events that were evaluated, and will be presented with its exact binomial CI. The validated algorithms will then be used in the study analyses to identify the primary endpoints of interest, and sensitivity analyses will be used to assess the impact of misclassification based on algorithm performance characteristics such as PPV. Additional operational details pertaining to the validation process will be described in a separate Endpoint Algorithm Development Plan.

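### The planned PPV correction for endpoint misclassification rescales incidence rates but cannot show any effect on the Duavee versus E+P hazard ratio

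*Protocol*

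**What the plan says.** Section 7.7.4 of the protocol lists three sensitivity analyses. The first two, on censoring at treatment switch and at cancer diagnosis, repeat the main analyses and so reach the HR. The third concerns "potential misclassification of the primary endpoints based on use of the developed algorithms". Its specification is confined to the incidence rate of each primary endpoint, which is to be adjusted using the PPV found in the validation work. The method is stated in one sentence: "This will be done by multiplying the number of observed cases by the PPV point estimate, and will be presented with a 95% CI".

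Appendix 3 says where the PPV comes from. The final algorithm is checked by "randomly selecting 200 women meeting the refined, score-based algorithm from the population of women using E+P HRT prior to the study period". The PPV itself "will be presented with its exact binomial CI".

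Section 7.7.1 presents incidence rates for each cohort, and section 7.7.6.3 estimates HRs from Cox models. The primary objective (section 6.2) has two parts, estimating incidence and comparing risk. No cohort-specific PPV and no corrected HR is described. No single sentence says that both cohorts share the PPV; this follows from reading sections 7.7.1 and 7.7.4 with Appendix 3.

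**The concern.** Section 7.3.2.1 itself warns that diagnosis codes alone may have low specificity for hyperplasia, so false positives are the expected problem. In a comparative safety study, the main question about them is what they do to the HR. An analysis that multiplies both cohorts' case counts by the same constant cannot answer it. A reader of the report would see a corrected rate in each cohort with the same relative risk as before, and could take this as evidence that the comparison is robust to misclassification. It would be only a consequence of the arithmetic.

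A second, smaller issue is that the correction uses the PPV point estimate, and nothing says that the uncertainty from a limited chart sample is carried into the corrected rate.

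**Working it through.** The protocol gives no PPV, corrected rate or corrected HR, so there is no stated figure to reproduce. Appendix 2 leaves both primary algorithms to be determined by validation. PPVs of 0.5 to 0.9 below are assumptions.

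**Inputs.** Table 1, third annual report: 399 hyperplasia and 80 cancer events in E+P users over 89,438 person-years; 5,400 Duavee users. A footnote to Table 1 assumes 10 months per Duavee user, giving 5,400 × 10/12 = 4,500 person-years. Appendix 3: 200 validation charts, read as per endpoint because section 7.3.2.1 develops the algorithms separately.

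**1. Cancellation.** The E+P hyperplasia rate is 399/89,438 = 4.46 per 1,000 person-years. At a rate ratio of 1.5, Duavee has 6.69 per 1,000 (about 30 cases).

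| Common PPV | E+P rate | Duavee rate | Ratio |
|---|---|---|---|
| 1.0 | 4.46 | 6.69 | 1.50 |
| 0.8 | 3.57 | 5.35 | 1.50 |
| 0.5 | 2.23 | 3.35 | 1.50 |

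The rates move and the ratio does not.

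**2. What false positives can do to the HR.** Set the observed E+P rate to 1, of which a share PPV is true and 1 − PPV false. If Duavee has the same false-positive rate, its observed rate is HR × PPV + (1 − PPV). Hence

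HR_obs = 1 + PPV × (HR − 1).

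For a true HR of 2.0:
- PPV 0.5: 1 + 0.5 = 1.5
- PPV 0.7: 1 + 0.7 = 1.7
- PPV 0.8: 1 + 0.8 = 1.8
- PPV 0.9: 1 + 0.9 = 1.9

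The inverse is HR = 1 + (HR_obs − 1)/PPV. Applied to the Year 3 hyperplasia upper limit of 1.39 in Table 1, it gives 1 + 0.39/0.8 = 1.49, 1 + 0.39/0.7 = 1.56 and 1 + 0.39/0.5 = 1.78.

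**3. Cohort-specific PPVs.** In general, true ratio = HR_obs × PPV_Duavee/PPV_E+P. With PPV_E+P = 0.8 and PPV_Duavee = 0.6, 0.7 or 0.9, the factor is 0.75, 0.875 or 1.125. With 0.6 in E+P and 0.8 in Duavee it is 1.33. Either direction is possible.

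**4. PPV sampling error.** With N cases and n charts, the relative SE of the corrected rate is sqrt(1/N + (1 − PPV)/(n × PPV)). Treating the PPV as fixed leaves sqrt(1/N). For E+P hyperplasia, N = 399 and n = 200:

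| PPV | Fixed PPV | With PPV error | Interval too short by |
|---|---|---|---|
| 0.8 | 0.0501 | 0.0613 | 18% |
| 0.7 | 0.0501 | 0.0682 | 27% |
| 0.5 | 0.0501 | 0.0866 | 42% |

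Simulated coverage of the nominal 95% interval (200,000 runs) is 89%, 85% and 74% respectively. For Duavee, expected hyperplasia cases at HR 1 are 4,500 × 399/89,438 = 20. The SE is 0.224 with the PPV fixed and 0.226 (PPV 0.8) or 0.235 (PPV 0.5) with its error, a shortfall of about 1% to 5%.

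If instead the multiplied count is treated as Poisson, the SE is sqrt(1/(N × PPV)). This is too small only when N exceeds n. At PPV 0.8:
- E+P hyperplasia: 0.056 against 0.061, 9% too short.
- E+P cancer (N = 80): 0.125 against 0.117, too wide.
- Duavee hyperplasia (N = 20): 0.250 against 0.226, too wide.

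**The case against.** Four replies deserve weight.

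- **The correction has a use.** It adjusts absolute rates, which serves the incidence half of the objective, and section 7.7.4 claims no more for it. This stands. The gap is that nothing is specified for the other half.
- **Appendix 3 promises more.** It says in general terms that sensitivity analyses will assess misclassification using performance measures such as the PPV, and defers operational details of validation to a separate plan. That leaves room for an HR analysis but does not specify one. The only method the protocol fixes is the one that cancels.
- **The bias is conditional.** A reader might infer that false positives must pull the HR toward 1. That needs equal false-positive rates in the two cohorts, which the document does not establish. With drug-related differences in coding or work-up, the direction is open. At a PPV of 0.9 the attenuation is small.
- **The interval method is not stated.** A reader might infer that the planned intervals are too narrow throughout. The protocol gives no CI method for the corrected rate and may leave it to an SAP. The shortfalls of 18% to 42% hold for one case count with the PPV treated as fixed. They are minor for Duavee, and the sign reverses for Duavee and E+P cancer under the Poisson treatment. What stands is that the protocol does not say the PPV's error is carried forward.

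**Conclusion.** The point holds for the comparison. As specified, the misclassification analysis scales each cohort's rate by one PPV per endpoint, estimated only in pre-study E+P users. It leaves the rate ratio unchanged and never reaches the Cox HR. This conclusion needs no numerical assumption beyond reading the shared PPV from sections 7.7.1 and 7.7.4 and Appendix 3 together.

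The possible size depends on an unknown PPV and on equal false-positive rates: a true HR of 2.0 would be observed as 1.5 to 1.9 for PPVs of 0.5 to 0.9. Without that equality, neither the size nor the direction can be given.

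On intervals, the supported statement is an omission with a material effect for E+P hyperplasia if the PPV is treated as fixed, assuming 200 charts per endpoint. The abstract's wording, "Medical records (for a random sample of 400 potential cases) will be used to refine and validate algorithms", could mean 400 records for both endpoints, leaving about 100 validation charts each. The PPV error would then be larger.

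**What to change.** In section 7.7.4, keep the corrected rates and add a quantitative bias analysis of the HR and its 95% CI for each primary endpoint:

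1. **Equal false-positive rates:** HR = 1 + (HR_obs − 1)/PPV_E+P, bounded below at zero. The bound is needed because the formula goes negative when HR_obs is below 1 − PPV. For example, the Year 1 hyperplasia lower limit of 0.44 in Table 1 gives 1 − 0.56/0.5 = −0.12 at PPV 0.5.
2. **Cohort-specific PPVs:** HR_obs × PPV_Duavee/PPV_E+P over a pre-specified grid.
3. **Uncertainty:** carry the binomial error of the validated PPV into the corrected rate and HR by bootstrap or delta method, and state which.

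The cost is a little more programming. The sensitivity intervals will be wider and depend on stated assumptions, so they should be labelled as a bias analysis beside the main HR.

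The pre-study validation set of 200 charts can stay as it is. Holding places in it for Duavee cases would conflict with Appendix 3, which validates the algorithm before it is used in the study.

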7.7.1. Main Analyses

The analyses will describe patients that initiate *Duavee* and the comparator E+P HRT cohort with respect to demographic and clinical characteristics as enumerated in [Section 7.3.4](#). Reasons for censoring will also be described by exposure group. Descriptive comparisons of the two cohorts will be done to document their differences at baseline and to identify potential confounders to be addressed in the propensity matching.

For each of the primary endpoints (i.e., endometrial hyperplasia and endometrial cancer), an IR will be calculated as the number of women meeting a claims-based algorithm for each outcome (first event only) divided by person-time at risk.

The IR and its associated 95% CI will be presented for each cohort overall and stratified by categorical patient age at cohort entry, total duration of *Duavee* or E+P HRT treatment (long vs. short), time since last exposure to *Duavee* or E+P HRT, exposure to local hormone therapy (See Appendix 2), and by presence (Y/N) of an osteoporosis diagnosis within the 90 days before or after initiation of *Duavee* or E+P HRT. Duration of treatment and time since last exposure will be categorized based on observed data distributions. The feasibility of these stratifications and of a possible analysis that stratifies simultaneously by duration of treatment and time since last exposure will be determined based on the number of observed safety events.

Further details of the validation process are described in Appendix 3 and will be contained in the separate Endpoint Algorithm Development Report.

Hazard ratios will be estimated that represent the relative risk associated with initiating *Duavee* as compared to E+P HRT. It is planned to conduct both crude (unadjusted) and adjusted analyses to assess the HR for each of the primary endpoints. Adjusted analyses will use propensity score matching to ensure comparability between treatment groups. Further discussion of the methods to be used in computing propensity scores is included in [Section 7.7.3](#).

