All Cancers (Malignancies)	At least two outpatient or one inpatient ICD-9-CM diagnosis code(s) in the following range: 140.xx-208.xx

*Endpoints will be identified in the NDI based on the presence of applicable codes listed as cause of death.

Algorithms for Claims-Based Identification of Safety Endpoints Identified in the Literature

Event type	Algorithm	Study Population	Validation
CHD (MI, fatal MI and sudden death)	MI defined as a hospitalization with ICD-9-CM code 410.xx (excluding 410.x2) with either (1) a length of stay between 3 and 180 days or (2) death if length of stay is less than 3 days.	HIRD patients receiving COX-2 inhibitors	In HealthCore data, this had a PPV of 88.4% (83.2% - 92.5%), which was higher in patients receiving COX2-inhibitors (92.3 versus 84.2%). Previously reported PPV of 94% in Medicare data.

CHD (MI, fatal MI and sudden death)
	
At least one occurrence of any of the following codes: ICD-9 diagnosis codes: 410 - 414, 433 - 438, 440 - 441, 4439. ICD-9 procedure codes: 3601 - 3609, 361, 362, 3812, 3813, 3818, 3925, 3926, 3929, 3950, 3990 CPT codes: 33510 - 33545, 33572, 34101 - 34111, 34201 - 34203, 35301, 35311 - 35381, 35390, 35454 - 35456, 35459, 35470, 35473 - 35474, 35482 - 35483, 35485, 35492 - 35493, 35495, 35533, 35541 - 35571, 35641, 35646, 35654, 92975, 92980 - 92984, 92995 - 92996
 
*Note - this includes codes for angina, MI, CABG and other procedures not included in the study definition.
	
HIRD patients receiving statins
	
Sensitivity of 96%, specificity of 93% and Kappa of 0.82 (PPV not calculated).

Stroke/TIA
	
An algorithm using primary discharge diagnosis codes for acute ischemic or hemorrhagic stroke (International Classification of Diseases, Ninth Revision, Clinical Modification codes: 430, 431, 433.x1, 434.x1, 436).
	
Medicare patients
	
Positive predictive value of 92.6% (95% confidence interval, 88.8%-96.4%), a specificity of 99.8% (99.6%-99.9%), and a sensitivity of 59.5% (53.8%-65.1%). An algorithm using only acute ischemic stroke codes (433.x1, 434.x1, 436) had a positive predictive value of 91.1% (95% confidence interval, 86.6%-95.5%), a specificity of 99.8% (99.7%-99.9%), and a sensitivity of 58.6% (52.4%-64.7%).

[figure not shown]

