Stroke/TIA	Diagnosis codes for acute ischemic or hemorrhagic stroke (International Classification of Diseases, Ninth Revision, Clinical Modification codes: 430, 431, 433.x1, 434.x1, 436) in any position	Medicare data linked to Women's Health Initiative patients	Specificity was 99.7%, negative predictive value was 99.7%, sensitivity was 82.8%, positive predictive value was 85.8%, and $\kappa=0.84$. Whereas specificity and negative predictive value exceeded 99%, sensitivity ranged from 75% to 88% and positive predictive value ranged from 80% to 90% across stroke definitions.
Stroke/TIA	
Ischemic stroke without TIA: (1) Hospitalization with ICD-9-CM diagnosis codes 433.x1, 434.x1, 436.x, 437.x1, 437.9x with either (1) a length of stay between 3 and 180 days or (2) death if length of stay is less than 3 days.
 
(2) Hospitalization with ICD-9-CM diagnosis codes 433.x1, 434.x1 with either (1) a length of stay between 3 and 180 days or (2) death if length of stay is less than 3 days.
	HIRD patients receiving COX-2 inhibitors	
In HealthCore data, algorithm 1 had a PPV of 87.4%, and algorithm 2 95.5% based on review of 175 cases
 
A prior study of Medicare beneficiaries saw a PPV of 96% for algorithm 1.

Breast cancer	
At least one inpatient diagnostic or procedure code for breast cancer: Malignant neoplasm of female breast: 174.0-174.9 Any Incisional breast biopsy: 85.12 Excision or destruction of breast tissue: 85.20 - 85.25 Subcutaneous mastectomy: 85.33-85.36 Mastectomy: 85.41-85.48
	Piedmont cancer registry	The sensitivity of the algorithm was 76.7%, positive predictive value 87.9%.

Breast cancer	At least one claim with ICD-9-CM code 174.xx, 233.0, 238.3 or 239.3.	HealthCore	Not formally validated, however in this study 766 medical records were reviewed to stage breast cancer. Internal communication was that medical records were not excluded based on lack of evidence of breast cancer. 13.4% of cases were stage zero, and 10.3% could not be staged.

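### The PPV-only correction of the primary incidence rates estimates the true rate times the algorithm's sensitivity; it is a lower bound, and whether it improves on the uncorrected rate is unknown

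*Protocol*

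**What the plan says.** In the main analysis (Section 7.7.1) the incidence rate of each primary endpoint is "the number of women meeting a claims-based algorithm for each outcome (first event only) divided by person-time at risk". Section 7.7.4 then plans three sensitivity analyses, the third addressing "potential misclassification of the primary endpoints based on use of the developed algorithms". For it, the rate "will be corrected for the PPV of the outcome algorithm as identified through validation", and the formula is given: "This will be done by multiplying the number of observed cases by the PPV point estimate, and will be presented with a 95% CI". No sensitivity term appears.

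Appendix 3 defines the PPV in the usual way: "The PPV will be calculated as the number of algorithm-identified events confirmed as true cases via medical record review", divided by all algorithm-identified events evaluated. The validation charts come from "randomly selecting 200 women meeting the refined, score-based algorithm". The training charts are also drawn only from women whom the preliminary algorithm (Algorithm 1) flags. Appendix 3 speaks in general terms of performance characteristics, naming PPV as an example, but specifies no correction for missed cases.

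**The concern.** A claims algorithm errs in two ways: it flags women who are not cases, and it misses women who are. Multiplying by the PPV deals with the first error only. Section 7.9 itself lists missing codes among the causes of outcome misclassification, and missing codes produce missed cases. Yet the only misclassification analysis planned for the primary endpoints can do nothing but lower the rate.

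The primary objective (Section 6.2) begins with estimating the incidence of endometrial hyperplasia and endometrial cancer. A rate described as corrected is likely to be read as the better estimate. In a safety study, an understatement that always runs in one direction should be labelled as such.

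**Working it through.** **Check of the PPV definition.** The thyroid cancer entry in Appendix 2 gives counts from which its stated PPVs can be reproduced as true positives over all positives. Code plus thyroidectomy: 50/(50 + 16) = 50/66 = 75.8%. Two codes within 90 days of thyroidectomy: 43/(43 + 4) = 43/47 = 91.5%. Both match.

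**Identity.** Let TP be the true cases flagged, O the observed (flagged) cases and T all true cases.

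- PPV = TP/O, so O = TP/PPV.
- Se = TP/T, so T = TP/Se.
- Uncorrected/true = O/T = Se/PPV.
- PPV-corrected/true = O × PPV/T = Se.
- Full correction: O × PPV/Se = T.

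**When the correction does harm (PPV below 1).** If Se ≤ PPV, the uncorrected rate is already at or below the truth, and the correction lowers it further. If Se > PPV, the corrected rate is further away when 1 − Se > Se/PPV − 1. Both cases are covered by Se < 2 × PPV/(1 + PPV).

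| PPV | Correction worse than none if Se is below |
|---|---|
| 0.5 | 0.667 |
| 0.6 | 0.750 |
| 0.7 | 0.824 |
| 0.8 | 0.889 |
| 0.9 | 0.947 |

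**Figures in Appendix 2.** Four sets state both values. For stroke by primary discharge code the entry reads "Positive predictive value of 92.6% (95% confidence interval, 88.8%-96.4%), a specificity of 99.8% (99.6%-99.9%), and a sensitivity of 59.5" per cent; for breast cancer, "The sensitivity of the algorithm was 76.7%, positive predictive value 87.9" per cent.

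| Algorithm | Se | PPV | Uncorrected/true | Corrected/true |
|---|---|---|---|---|
| Stroke, primary discharge diagnosis | 0.595 | 0.926 | 0.643 | 0.595 |
| Acute ischemic stroke codes only | 0.586 | 0.911 | 0.643 | 0.586 |
| Stroke, any position | 0.828 | 0.858 | 0.965 | 0.828 |
| Breast cancer | 0.767 | 0.879 | 0.873 | 0.767 |

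In all four the corrected rate is further from the truth.

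The thyroid counts give sensitivity only relative to the 52 cases found by the diagnosis code, and they point both ways. Code plus thyroidectomy: Se 50/52 = 0.962, and the rate moves from 66/52 = 1.269 to 0.962 of the truth, which is closer. Two codes within 90 days: Se 43/52 = 0.827, and the rate moves from 47/52 = 0.904 to 0.827, which is further away.

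**Illustration on the protocol's hyperplasia projection.** Table 1, third annual report: 399/89,438 = 4.46 per 1,000 person-years. Se and PPV below are assumptions, and the pilot count is treated as if the final algorithm had produced it.

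| Assumed Se | Assumed PPV | Uncorrected | × PPV | × PPV/Se (true) |
|---|---|---|---|---|
| 0.60 | 0.90 | 4.46 | 4.02 | 6.69 |
| 0.95 | 0.50 | 4.46 | 2.23 | 2.35 |

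In the first row the planned correction makes matters worse; in the second it brings the rate close to the truth.

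**The case against.** The strongest reply is that nothing shows harm to the rates actually being corrected. Appendix 2 lists both primary algorithms as still to be determined, with no Se or PPV. The pairs above belong to secondary endpoints, for which Section 7.7.1 rules out PPV correction. Section 7.3.2.1 expects low specificity from hyperplasia diagnosis codes alone and calls the endometrial cancer codes nonspecific. Many false positives are the setting in which a PPV correction tends to help.

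All of this stands. A reader might infer from the stroke and breast cancer figures that the planned correction will move the endometrial rates away from the truth. The documents do not support that inference, and the code-plus-thyroidectomy figures go the other way. The specificity remark, however, concerns raw codes. The correction will be applied to a refined, thresholded algorithm, whose balance of PPV and sensitivity is not yet known.

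A second reply is that the protocol openly calls this a correction for the PPV, treats it as a sensitivity analysis and keeps the uncorrected rate as the main result. That limits the seriousness. It does not change what the formula estimates, and this is the only analysis that Section 7.7.4 offers for misclassification of the primary endpoints.

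A reader might also suppose that the ROC step in Appendix 3 already supplies the missing sensitivity. It does not. The share of confirmed training cases above the threshold comes from the charts used to fit the model and set the cut-off, and it cannot see cases that Algorithm 1 missed.

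**Conclusion.** The point holds for what the formula estimates. Provided that the validation PPV, obtained in E+P HRT users before the study period, carries over to both study cohorts, the PPV-only rate has expectation true rate × Se. It understates incidence by the fraction 1 − Se whenever Se is below 1. It is further from the truth than no correction when Se < 2 × PPV/(1 + PPV), a condition that a good algorithm can meet: at PPV 0.9, any Se below 0.947.

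For endometrial cancer and hyperplasia the net effect of the correction, helpful or harmful, is unknown. The planned chart samples cannot settle it, because they contain only algorithm-positive women. This is an inexpensive improvement to a labelled sensitivity analysis, not a defect in the main analysis.

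**What to change.** In Section 7.7.4:

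- Label the PPV-only figure as a lower bound, namely the rate of confirmed, algorithm-detected cases.
- Add a bias analysis that reports observed cases × PPV/Se over a stated range of assumed sensitivity, for example 0.6 to 1.0, beside the uncorrected rate. With an assumed PPV of 0.8 and the hyperplasia projection above, the range would run from 4.46 × 0.8/1.0 = 3.57 to 4.46 × 0.8/0.6 = 5.95 per 1,000 person-years, around the uncorrected 4.46.
- The share of confirmed training cases above the ROC threshold may inform the range, but only as an optimistic upper bound on sensitivity.

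The cost is a little more analysis work, and a corrected rate shown as a range instead of a single figure. No further charts are needed.
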